17.1 Roland-Morris Low Back Pain and Disability Questionnai	
17.2 Mobility Test	
17.3 Instructions for Patch Use	

Study Synopsis

Title	A phase IIIB randomized, open label, two arms and parallel group clinical trial to			
	assess the efficacy and safety of FIRTECH (Infrared Therapy Patch), for treating			
	patients suffering from mild to moderate acute low back pain.			
Short Title	Efficacy and Safety of FIRTECH in Patients with Mild to Moderate Acute Low			
	Back Pain			
Protocol Numbers	LPS16453			
Study Sponsor	SAR&D Sanofi-Aventis Recherche & Développement			
Principal Investigator	TBD			
Study Design	This is an open label, randomized, patch arm vs. and no-patch control arm, clinical			
	trial.			
Study Duration	12 months			
Study Center(s)	Approximately 10 centers in Germany and Italy			
Objectives	Primary: To assess the efficacy of the ITP FIRTECH for treating subjects			
	suffering from mild to moderate acute low back pain			
	Secondary:			
	To assess the efficacy of ITP FIRTECH on the subject disability.			
	To assess the efficacy of ITP FIRTECH on the degree of subject mobility.			
	To assess the safety of ITP FIRTECH			
Number of Subjects	200 enrolled subjects: 180 evaluable subjects (90 in each arm).			
Main Inclusion /	Inclusion:			
Exclusion Criteria	1. Male or female subjects who are ≥18 years and < 65 years.			
	2. Subjects suffering from mild to moderate acute low back pain.			
	• Low back pain (lumbar back pain) is defined as pain in the back from the			
	level of the lowest rib down to the gluteal fold.			
	• Acute episode is defined as acute pain with less than 1 month duration.			
	• With intensity ≤ 6 on 0-10 Numerical Rating Scale (NRS)			
	Exclusion:			
	1. Subjects suffering from any neurological pathology which could be			
	responsible for the pain.			
	2. Subjects suffering from leg pain irradiation.			
	3. Subjects suffering from chronic lumbar pain of any etiology.			
	4. Subjects with chronic arthrosis and neurological symptoms			
	5. Subjects experiencing recent significant trauma (i.e., injury related to a fall from a height or motor vehicle crash, or from a minor fall or heavy lifting in			
	a subject with osteoporosis or possible osteoporosis),			
	6. Subjects with major or progressive motor or sensory deficit, new-onset			
	bowel or bladder incontinence or urinary retention, loss of anal sphincter			
	tone, saddle anesthesia, history of cancer metastatic to bone, and suspected			
	spinal infection.			
	7. Subjects clinically diagnosed with anxiety and/or depression			
	8. Subjects using any medication for their pain within the last 48 hours within			
	enrollment into the study			
	9. Subjects taking any systemic medication for their pain within the last 24 hours			
	(48 hours for diclofenac or corticosteroids).			

Γ	T					
	10. Subjects currently using recreational or illicit drugs or with a recent history					
	of drug or alcohol abuse or dependence.					
	11. Subjects with any other medical condition that would interfere with efficacy and safety assessments based on investigator's judgment.					
	12. Subjects having received non pharmaceutical LBP treatment					
	(physiotherapy, heat treatment or massage) within 12 hours prior enrolling					
	13. Subjects having received spinal injection back pain treatment within 6 months prior enrollment					
	14. Subjects having received surgery due to back pain or rehabilitation due to					
	back pain in the last 12 months					
	15. Subjects with a known sensitivity to paracetamol					
	16. Known cutaneous hypersensitivity to plaster					
	17. Subjects participating in another clinical study within the past 30 days					
	18. Subjects who are pregnant or breastfeeding. Contraception is mandatory					
	19. Subjects having damaged, non-intact, or scarred skin in or near the point of					
	patch application.					
	20 Subjects having a known skin sensitivity.					
	21. Subjects having impaired blood circulation.					
Study Device	FIRTECH Infrared Therapy Patch					
Duration of Device	5 days					
Exposure						
Reference Therapy	None					
Endpoints	Primary: A Numerical Rating Scale (NRS) responder at Day 5 at the on-site					
	evaluation (defined as $\geq 30\%$ decrease from baseline of the instantaneous pain					
	and no rescue medication).					
	Secondary:					
	Normalized Sum of Pain Intensity Difference (PID, which equals the NRS					
	change from baseline) over 5 days (SPID ₀₋₅).					
	Roland-Morris Disability Questionnaire (RMDQ) score improvement (%)					
	from baseline to Day 5.					
	Mobility evaluation: change from baseline to Day 5					
	Time to reach acceptable pain					
	Other secondary endpoints					
	• Time to reach no pain (NRS = 0)					
	Time course of PID over time from baseline to Day 5 on-site evaluation The state of PID over time from baseline to Day 5 on-site evaluation The state of PID over time from baseline to Day 5 on-site evaluation					

1.4.3 Statistician

ICON Clinical Research

2 Introduction / Background and Rationale

Low back pain (lumbar back pain) is defined as pain in the back from the level of the lowest rib down to the gluteal fold. An acute pain episode is defined, as acute pain with less than 1 month duration, however, there is non consistency across international guidelines to define acute versus chronic pain [1].

Back pain affects between 60% and 80% of all people at some time in their life. Fifteen to forty-five percent of adults suffer LBP, and 1/20 (5%) people present to a healthcare professional with a new episode. Low back pain is most common between the ages of 35 to 55 years. About 30% of European workers reported that their work caused LBP. Prevalence varies across countries, ranging from 13% to 44%. In 50% to 80% of people with acute LBP, symptoms recur within 1 year, indicating a high recurrence rate. Thirty-three percent of people still endure moderate-intensity pain and 15% experience severe pain 1 year after the initial episode. Fifty percent of episodes nearly completely resolve within two weeks, and 80% by six weeks^[2].

Patients with peripheral pain may achieve pain relief with currently recommended first-line oral treatments, which are also associated with systemic adverse events. Topical treatments are currently considered second-line options, but their safety profiles are better than oral treatments.

Infrared Therapy Patches (ITP) are Class I Medical Devices and can relieve painful symptoms without the use of drugs. The effects duration varies according to each person's state of health.

The objective of the LPS16453 study is to determine the efficacy and safety of the ITP FIRTECH compared with no-patch control arm for treating acute mild to moderate low back pain.

The study is designed as open label with a no-patch control arm. The following items had been taken into account in this decision:

- It is necessary to provide controlled data in support of the therapeutic effect. These types of body pain are self-limiting and many patients will improve even without any treatment. Just observing treated patients and recording their improvement (post- versus pretreatment) will not allow description of the level of effect coming from the patch.
- There is no real sham (placebo). The double blind approach is impossible to reach. In fact, the active compound is part of the tissue structure:
 - O The purpose of the clinical study is to prove the efficacy of re- emitted IR energy for pain relief. This is not specifically limited to the IR re-emitted from particles such as titanium dioxide. Other components of the patch such as the fabrics also re-emit IR.
 - The efficacy of the patch maybe therefore not only be associated with the used ceramic particles, but with the entire patch respectively re-emitting IR.
 - o In theory, the placebo of the IR emitting patch should be designed as a non-emitting patch (i.e., all materials of construction have zero emissivity). All materials emit and re-emit IR (to various degrees). Therefore, a completely non-emitting placebo device cannot be produced/manufactured.
 - The similar tissue has effect of reflection of the emitted infrared radiation; this patch would not be a placebo in the true sense of the definition.

All study participants have access to rescue medication. Treatment is available and even
a delay in the treatment will not automatically result in a worsening of the medical
condition.

The study will be performed according to all local regulations.

3 Device Description

The device consists of a patch patch consists of two layers, a TNT (Polypropylene) support coated with an adhesive containing Titanium Dioxide, printed in the upper part. It contains a film of transparent polyethylene terephthalate (PET) that serves as a protective support for the adhesive layer. This protective film is pre-cut to facilitate easier application of the patch to the skin. Titanium dioxide belongs to the category of molecule with a high emittance, the intrinsic ability to "receive" and "re-emit" specific wavelengths. Specifically, the emittance of titanium dioxide is located in a range of infrared (IR) frequencies that notoriously have an interesting therapeutic aspect.

Table 1. FIRTECH Infrared Therapy Patch Composition

	 				
Support	Non woven fabric – white (Polypropylene) [CAS #9003-07-0]				
Adhesive	Polyacrylate [CAS #25133-97-5]				
Protective support	Polyethylene terephthalate [CAS #25038-59-9]				
Chemical element	Titanium Dioxide [CAS #13463-67-7] and Synthetic wax (poly(alpha-olefins, alkenes, C>10 alpha-, polymerised))				

The medical device under review contains no analgesics, no tissues or blood products or cells, or their derivatives, of human or animal origin.

All investigational devices will have the following label statement: **CAUTION** – **For Investigational Use Only**.

4 Device Accountability

4.1 Device Receipt

Devices will be shipped directly to the investigator from the Sponsor. Upon receipt by the Investigator, devices will be inventoried and stored as per Section 4.2 below. For inventory purposes, each device will be assigned an inventory number which will be recorded on an inventory log.

4.2 Device Storage

Devices will be stored in a restricted access location with access by the Investigator or designee only. Devices will be stored under ambient conditions. There are no special handling requirements for this device.

4.3 Device Dispensing

Devices will be dispensed by the Investigator, or designee, as needed for each Subject. For device accountability, device inventory numbers will be recorded on the Subject's case report form, and the Subject's ID number will be recorded on the inventory log. The inventory log will be reconciled with Subject records during the monitoring visits and this reconciliation will be noted on the device inventory form, and signed and dated by the study team designee.

4.4 Device Disposition

At the end of the study period, the Subject will return to the investigational site to have the patch removed. If the patch is removed or if it peels off prior to its scheduled removal, Subjects are instructed to apply a new patch at home. All the used and unused patches have to be returned to the investigational site at Visit 2

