7.6 Clinical Procedures

The study will be performed in Investigational Sites and an online e-diary will be used.

A total of 2 site visits and 1 phone contact are planned during a maximum of 5 days of treatment and 6 days of total study duration.

7.6.1 Day 1, Visit 1

Clinical procedures on Day 1, Visit 1 include the following:

- Verification of eligibility
- Informed Consent Signatures
- Local Physical Examination

- Collection of Vital Signs to include: Respiratory rate, Heart rate, Temperature, Blood Pressure
- Collection of Demographics to include: Age, Gender
- Collection of relevant medical history and concomitant medications
- On-line daily e-diary will be explained and activated
- Urine pregnancy testing (for women of childbearing potential only)
- Causes and/or circumstances triggering the acute back pain
- Baseline Subject symptom self-assessment
 - Pain Perception (NRS): Numerical Rating Scale^[3] for pain assessments at baseline and at defined time points: 0-10 NRS; '0' representing "no pain" and '10' representing "worst pain imaginable
 - Instantaneous: pain at the moment of the evaluation
 - Average pain in the previous 12 hours.
 - Worst pain in the previous 12 hours
 - Least pain in the previous 12 hours
 - o Roland-Morris Disability Questionnaire (RMDQ)^[5]
- Baseline mobility assessment (physician)
- Randomization:
 - O Arm A: ITP FIRTECH: Patch application according to the instruction for use in Section 17.3: The patch has to stay in position for 5 days. If the patch is taken-off or if it fell off during the study duration, the subject is invited to replace the patch at home following the instruction for use. Subject is allowed to take-off the patch at any time in case of severe skin itchiness, irritation, or skin reaction and in this case the subject has to contact the study center.
 - o Arm B: no-patch: Subjects will be informed that they will not be assigned a patch in this study.
- All subjects are informed that rescue mediation (paracetamol, up to 2 g per day), while not encouraged, is allowed if necessary.
- All subjects will be informed of the prohibited medications.
- If rescue medication is taken, the exact moment(s) and the dose(s) have to be indicated in the e-diary.
- An explanation will be provided on how to use e-diary at home and providing all necessary access credentials
- All subjects will be requested to avoid bed rest and will be recommended to continue with a normal daily life activity.

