7.8 Study Timetable / Schedule of Events

Table 3. Schedule of Events

Visits	V1	At	V2	Phone	Unsch	Notes
		Home		Call		
Days	D1	D1 to	D5	D6		
		D5				
Eligibility verification	✓					
Informed Consent	✓					
Demographics /	✓					
Medical History						
Physical Exam	✓		✓		✓	
Vital Signs	✓				✓	

Visits	V1	At	V2	Phone	Unsch	Notes
		Home		Call		
Days	D1	D1 to D5	D5	D6		
Urine Pregnancy Test	√					For women of child-bearing potential only
E-diary Activation	✓					
Randomization	✓					
E-diary Completion	✓	√ *	√ **			*2 times per day at the same times **On-site evaluations
Pain perception	✓	✓	✓			
Pain-relief evaluation		✓	✓			
Pain acceptable perception		~	√			
Rescue Medication Needed		V	√			
Roland-Morris Disability Questionnaire	√		√			
Mobility assessment	√		√			Schober's Test or Fingertip- to-floor test
Adverse Event assessment	√	~	√	√	√	
Patch application / removal	✓		✓		✓	Patch(es) has(have) to be used for 5 days. If the patch is taken-off for a safety reason, the subject has to contact the study center. If the patch falls off, the subject has to replace it as soon as possible. The subject will complete the diary card, informing about the patch replacement, the reason of change, and the time spent with no patch.
Concomitant therapies	✓	✓	✓	✓	✓	
e-diary review			√		√	

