9.2.1 Anticipated Risks / Risk Mitigation

The anticipated risks associated with this clinical protocol include minor skin hypersensitivity reactions such as skin irritation due to the patch adhesive. This risk is considered minor and will be assessed at patch removal and/or if the patch is removed prior to study completion. Risk is mitigated by patch removal as soon as such reactions are detected.

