In case the first patch falls off, apply the second patch to the same area, closely following the instructions again.

Recommendations:

- The patch is water-resistant, which means that it remains active even when it is wet. You can shower with it. After you shower, gently pat the patch dry with a towel without rubbing.
- Avoid very hot water, sauna, steam bath, bathing or swimming, as this can cause the patch to peel off.
- Avoid to wear tight clothes that can increase the risk of the patch peeling off.
- Avoid to apply any oily substance on the patch area during the time when you are wearing the patch

How to peel off the patch on Day 5:

Remove the patch by gently lifting one end and dispose as household waste. Do not reuse..

Warnings

- Store at room temperature.
- For external use only.
- Apply only to clean, dry, undamaged skin.
- Discontinue treatment in the event of evident irritation or hypersensitivity to the product.
- In case of specific blood circulation or muscular problems, seek the advice of your doctor before applying the plasters.
- Keep out of the reach of children.
- The patch should only be used by adults (> 18 years old).
- Do not use if the packaging is broken or punctured since damaged packaging could compromise efficacy and safety of the product
- Should not be used for pregnant or lactating women
- (Read the instructions for use)

SIGNATURE PAGE

IRPATCH Study #LPS16453; Version 4 / 22 Jul 2022

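### Section 4.4 has subjects put on a new patch after any early removal, without excepting skin reactions, which conflicts with Section 17.3 and the Schedule of Events

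*Protocol*

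**What the plan says.** Protocol Section 4.4, in the device accountability chapter, states: "If the patch is removed or if it peels off prior to its scheduled removal, Subjects are instructed to apply a new patch at home".

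Section 7.6.1 (Arm A) says: "If the patch is taken-off or if it fell off during the study duration, the subject is invited to replace the patch at home", adding that the instructions for use are to be followed. It then says: "Subject is allowed to take-off the patch at any time in case of severe skin itchiness, irritation, or skin reaction", and that a subject who does so must get in touch with the site. It also provides two spare patches. The evening diary item in Section 7.6.2 records patch removal together with application of a new one, refers to Section 17.3, and asks for the reason.

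The note in the Schedule of Events (Section 7.8, Table 3; repeated in SAP Section 2.3, Table 1) separates two cases: "If the patch is taken-off for a safety reason, the subject has to contact the study center" and "If the patch falls off, the subject has to replace it as soon as possible".

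Section 9.2.1, on minor skin hypersensitivity reactions, says: "Risk is mitigated by patch removal as soon as such reactions are detected". The warnings in Section 17.3 say: "Discontinue treatment in the event of evident irritation or hypersensitivity to the product". Once the patch has been worn, Section 17.3 calls for a second one only if the first falls off.

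Section 9.3 names minor skin irritation at the application site as the anticipated adverse event and gives its frequency as unknown.

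**The concern.** A subject who removes the patch because of evident irritation cannot follow both Section 4.4 and Section 17.3: one calls for a new patch, the other for stopping. Prompt removal is the only mitigation the protocol states for the only device risk it names, and a literal reading of Section 4.4 reverses it. The spare patches mean that re-application needs no visit.

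Safety is a secondary objective, and this trial is where the unknown frequency of irritation would be described. If sites follow different sections, similar reactions may be followed by different exposure, and the safety data would partly reflect which section was read.

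**Working it through.** No statistical calculation applies; the check is a comparison of every passage on removal, replacement and skin reaction.

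| Section | Trigger for early removal | What follows |
|---|---|---|
| 4.4 | Any removal, or peeling off | New patch at home; no exception |
| 7.6.1, replacement sentence | Taken off or fell off | Replacement is invited, following the instructions for use |
| 7.6.1, skin sentence | Severe itchiness, irritation or skin reaction | Site contact; silent on a new patch |
| 7.8 note and SAP 2.3 | Safety reason | Site contact; silent on a new patch |
| 7.8 note and SAP 2.3 | Falls off | Replacement required |
| 9.2.1 | Detection of a (minor) reaction | Removal; silent on a new patch |
| 17.3 | Evident irritation or hypersensitivity | Stop treatment |
| 17.3 | Falls off | Second patch |

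*What follows removal.* Sections 4.4 and 17.3 give opposite directions for a patch removed because of evident irritation. Section 4.4 also disagrees with the Schedule of Events note, which requires replacement only for a patch that falls off. Section 7.6.1 and the note add a duty to contact the site, but neither says whether a new patch may go on before or after that contact, and no section tells the site what to advise. The exit criteria in Section 6.4.7 leave withdrawal from the study for an adverse event to the subject or the investigator. They do not address stopping the patch while remaining in the study.

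*When to remove.* There are four wordings: severe itchiness, irritation or reaction (7.6.1), a safety reason (7.8), detection of a reaction described as minor (9.2.1), and evident irritation (17.3). They need not coincide for a mild reaction.

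*Possible size.* Section 6.4.1 gives 200 randomised 1:1, so 200 / 2 = 100 in the patch arm. The frequency of irritation is not given. For illustration only:
- 2% assumed: 100 × 0.02 = 2 subjects
- 5% assumed: 100 × 0.05 = 5 subjects
- 10% assumed: 100 × 0.10 = 10 subjects

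These are subjects who might have a reaction and so meet the conflicting texts. They are not a forecast of how many would re-apply. Two spares put a ceiling of two re-applications on any one subject.

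*Effect on the analysis.* Protocol Section 8.3.2.1 and SAP Section 5.1.8.1 count subjects with at least one event. A reaction that led to removal is already counted, whether or not a new patch follows. Re-exposure could change the maximum severity, which the SAP does tabulate. No summary of the duration or outcome of skin reactions is planned. The SAP tabulates events leading to study discontinuation but lists none for patch discontinuation, so subjects who stop the patch and stay in the study are not shown separately.

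**The case against.** A reader might infer that the protocol as a whole sends a subject with irritation straight back onto the device. The documents do not support that. The unqualified instruction is in Section 4.4, an accountability section. Section 7.6.1 only invites replacement, points to the instructions for use (which carry the warning to stop), and treats skin reactions separately: "in case of severe skin itchiness, irritation, or skin reaction and in this case the subject has to contact the study center". The Schedule of Events note likewise separates safety removal from falling off.

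A reader might also infer that Section 7.6.1 obliges a subject with a mild reaction to keep the patch on. That goes too far. The sentence is permissive, and *severe* may qualify only the itchiness. Whether mild redness would count as *evident* under Section 17.3 is equally open.

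Other safeguards exist. The diary captures adverse events, and patch replacement with its reason and the time without a patch. There is a local examination at Visit 2, a safety call on Day 6, and withdrawal at the investigator's judgement. The protocol calls the risk minor, anticipates no serious events, and limits wear to 5 days.

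All of this stands and limits the consequences. It does not remove the conflict between Sections 4.4 and 17.3, and it does not supply the missing statement on whether a new patch may be applied after a safety removal.

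**Conclusion.** The point holds as an internal inconsistency of moderate severity. Section 4.4 contradicts Section 17.3 and the Schedule of Events note on what follows removal for a skin reaction. Sections 7.6.1 and 7.8 leave that step unstated, and the removal trigger is worded in four ways. Read literally, Section 4.4 allows re-exposure after the only anticipated device harm.

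The primary endpoint is not affected. The effect on adverse event incidence is likely small; maximum severity and exposure after a reaction are the quantities that could vary with the section followed. Reasons for patch changes are recorded, so that information is not lost. The conclusion rests on the wording alone and on no assumed event rate.

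**What to change.** Reconcile protocol Sections 4.4, 7.6.1, 7.6.2, 7.8, 9.2.1 and 17.3, and the repeated note in SAP Section 2.3, so that they state:

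1. one trigger for removing the patch because of a skin reaction;
2. one rule for what follows such a removal, including whether and when a new patch may be applied and how this relates to the contact with the site;
3. separately, the replace-at-home rule for a patch that falls off or peels, as the Schedule of Events note already does for falling off.

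Use the same words in the instructions given to subjects. The sponsor's medical team must choose the trigger and the rule; this review does not say which is right. The cost is protocol, SAP and leaflet wording, with no added visits, staff or data collection.
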